# **Study Protocol**

## **Development of Pneumonia Due to Alveolar Glucose Levels in Systemic Hyperglycemia**

Version: 2  
Date: 08/01/2017

1. General study design:

Monocentric prospective clinical observational study

2. Schedule:

Inclusion of the first patient: 08/01/2017

Inclusion last patient: 12/31/2018

Close the database: 01/31/2019

End of the statistical evaluation: 06/31/2019

3. Study endpoint, duration of study:

The primary endpoint of the study is the incidence of pneumonia

4. Sample size calculation:

The sample size estimate was based on the assumption that in the investigated patient population the occurrence of pneumonia could be expected in 10% of the patients. Thus, for an unconnected sample, a ratio (m) of 0.9 controls per incidence of pneumonia. In a previous study (Bacterial respiratory tract infections are promoted by systemic hyperglycemia after severe burn injury in pediatric patients, Kraft et al., Burns, 2014, May), it was found that the mean values ( $\delta$ ) of both groups for glucose differed by about 30 mg / dL in the mean with a standard deviation ( $\sigma$ ) of 20 mg / dL. Under the same conditions, 14 controls and 16 patients with pneumonia are needed to reject the null hypothesis with a probability (power) of 0.9.

The occurrence of the first type error ( $\alpha$ ) was set at 0.01. Design: Independent  $\alpha = 0.01$ ; power = 0.9;  $\delta = 30$ ;  $\sigma = 20$ ;  $m = 0.9$ ;  $n = 16$ ;

t-test confidence interval width = 40.68604

Calculated with PS Power and SampleSize Calculator Version 3.0,

<http://biostat.mc.vanderbilt.edu/PowerSampleSize>

5. Selection of the study population:

Patients undergoing elective cardiac surgery matching inclusion and exclusion criteria

6. Subsequent exclusion of study patients:

Reasons for a subsequent exclusion of the patient only apply if subsequently it is determined that not all inclusion criteria are met or exclusion criteria that were not initially recognized. These patients are also excluded from the documentation.

7. Documentation / Evaluation:

All study-relevant data are recorded in the provided documentation sheets by the responsible study physicians and, if necessary, the study assistants. The study forms are digitized and stored in the in-house EDP system in compliance with the safety guidelines using the programs Microsoft Excel® and Access®. Radiological images are stored in digital form, preferably in TIFF or raw data format. The statistical analysis is carried out by means of the programs Sigmastat® and SigmaPlot®.

The statistical evaluation is carried out on the one hand with regard to the cut-off value of the glucose threshold of the lung by means of Receiver Operating Characteristic (ROC). This is used to validate our findings in comparison to the already existing preliminary studies. The evaluation of dichotomous variables is performed by Chi Square Test or, if necessary, by Logistic Regression Analysis.

Constant features are compared using Student's t-test, analysis of variance between the groups. With regard to the presence of disturbing variables between the two groups, the formation of subgroups, possibly a matching by means of a propensity score, is planned.

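### The sample size uses 0.9 controls per pneumonia case, but the assumed 10% rate implies 9; the printed 16 cases and 14 controls do not fit that rate, and no total enrolment is given.

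*Protocol*

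**What the plan says.** Protocol section 4 (Sample size calculation) starts from the assumption that "the occurrence of pneumonia could be expected in 10% of the patients". The next sentence derives the group ratio from it: "Thus, for an unconnected sample, a ratio (m) of 0.9 controls per incidence of pneumonia". With a difference of 30 mg/dL, a standard deviation of 20 mg/dL, alpha 0.01 and power 0.9, the section concludes that "14 controls and 16 patients with pneumonia are needed to reject the null hypothesis", and it prints "t-test confidence interval width = 40.68604". Whether the test is one- or two-sided is not stated. The SAP repeats the paragraph with the same figures.

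Section 1 describes the design as "Monocentric prospective clinical observational study" and section 5 gives the population as "Patients undergoing elective cardiac surgery matching inclusion and exclusion criteria". Section 3 states: "The primary endpoint of the study is the incidence of pneumonia". Under section 8, patients consent and are included before surgery and are then examined daily for signs of pneumonia. Section 2 gives dates for the first and last inclusion. Neither document gives a number of patients to enrol.

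**The concern.** The ratio m is defined as controls per case and is presented as a consequence of the 10% rate. At 10%, nine patients remain free of pneumonia for each one who develops it. The value 0.9 is the share of patients without pneumonia, entered where the ratio belongs.

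Pneumonia develops after inclusion, so the investigator cannot fix the case-to-control ratio at enrolment; the cohort's event rate sets it. The printed split of 16 to 14 would arise by itself only if about half the patients developed pneumonia.

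What is at stake is the recruitment target. The purpose of the calculation is to say how many patients to recruit. With a ratio that contradicts its own premise and no stated total, a reader cannot tell whether about 80, 90 or 160 patients are intended, or even the 30 obtained by adding the two groups.

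**Working it through.** **Inputs** (Protocol section 4, repeated in the SAP): alpha = 0.01, power = 0.9, delta = 30, sigma = 20, m = 0.9 controls per case, pneumonia rate 10%. Two-sided testing is my assumption; step 1 tests it.

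**1. Reproduce the printed figures with m = 0.9.** For n cases and mn controls, iterate

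n = (sigma/delta)² × (1 + 1/m) × [t(1 − alpha/2, df) + t(0.9, df)]², with df = n(1 + m) − 2.

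- Two-sided: df = 27.66, so n = 0.4444 × 2.1111 × (2.7657 + 1.3129)² = 15.61 cases and 0.9 × 15.61 = 14.05 controls.
- 99% interval width = 2 × t(0.995, df) × sigma × √(1/n + 1/(mn)) = 2 × 2.7657 × 20 × √(1/15.609 + 1/14.048) = 40.68603. The document prints 40.68604.
- One-sided: 13.63 cases, rounded up to 14 rather than 16, with a 99% width of 44.05. Neither printed figure is matched.

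The calculation was therefore run two-sided and with 0.9. The 0.9 is not a misprint of a run made with 9.

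**2. Ratio implied by the premise.**

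- 10% rate: m = 0.90/0.10 = 9.
- Rate implied by m = 0.9: 1/(1 + 0.9) = 52.6%. The printed groups give 16/30 = 53.3%.

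**3. Same calculation with m = 9.** df = 74.52, so n = 0.4444 × 1.1111 × (2.6434 + 1.2930)² = 7.65 cases and 68.87 controls, 76.5 patients in total, width 40.3. Rounded up, this is 8 cases and 8 × 9 = 72 controls, 80 patients, width 39.4.

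**4. Power** (noncentral t, two-sided alpha 0.01, standardised difference 30/20 = 1.5):

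| Cases | Controls | Total | Power |
|---|---|---|---|
| 16 | 14 | 30 | 0.899 |
| 7 | 63 | 70 | 0.864 |
| 8 | 72 | 80 | 0.914 |
| 16 | 144 | 160 | 0.999 |
| 3 | 27 | 30 | 0.399 |

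The last row is what 30 enrolled patients would yield on average at 10%. The documents do not say that 30 is the total.

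**5. Random number of cases.** In a cohort of N patients the case count is Binomial(N, 0.1).

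| N | Power averaged over the case count | Chance of reaching the case target |
|---|---|---|
| 80 | 0.865 | 0.55 (at least 8) |
| 90 | 0.906 | 0.69 (at least 8) |
| 160 | 0.994 | 0.54 (at least 16) |

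Averaged power first reaches 0.90 at 89 patients (0.899 at 88, 0.902 at 89). For 16 cases the expected enrolment is 16/0.10 = 160; a 90% chance of at least 16 needs about 210.

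**The case against.** The strongest defence is that a near-balanced comparison was intended: all cases against a similar number of selected controls, with samples stored for later analysis. In that case 16 and 14 could stand and only the derivation sentence would be wrong. The text does not support this reading. The ratio is drawn from the 10% rate, not from a sampling choice; the sample is described as unconnected; no rule for selecting controls appears; and on matching, Protocol section 7 says only that "possibly a matching by means of a propensity score, is planned", to deal with confounders. Even under that reading, 16 cases at 10% require about 160 enrolled patients, a figure neither document gives. The possibility does mean the sponsor should first say which comparison is intended.

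Three narrower objections have some force.

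- Recruitment is bounded by the inclusion dates in section 2, so it is not open-ended. The dates supply no number, however.
- Reproducing the output shows that the arithmetic follows from the printed inputs. It does not show that a comparison of mean glucose is the right basis for a study whose primary endpoint is incidence, or that it covers the ROC cut-off in section 7. This point makes no claim on those matters.
- Moving to 8 cases would leave few events for the ROC, logistic regression and propensity-score analyses. That is a reason the sponsor might keep 16 as the target; it does not justify m = 0.9.

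It is also fair that power for the stated t-test is not in danger: the correct ratio lowers the number of cases needed.

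**Conclusion.** The concern holds and must be fixed. The ratio in both documents contradicts the rate from which it is derived, by a factor of ten (0.9 against 9). With the other inputs unchanged, the requirement moves from 16 cases and 14 controls to 8 cases and 72 controls. The implied enrolment is 80 patients at exactly 10%, about 90 when power is averaged over the random case count, or about 160 on average if 16 cases is kept; the documents state none of these.

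The fault is a wrong input and a missing enrolment figure, not low power. Sixteen cases with 14 controls give 0.899, and more controls give more. Power would be low, at about 0.40, only if 30 patients in total were meant.

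These results take the printed difference, standard deviation, alpha and 10% rate as given and assume a two-sided test, which is the version that reproduces the printed figures. A one-sided test with m = 9 gives 7 cases and 63 controls, which leaves the conclusion unchanged.

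**What to change.** The sponsor should first decide the case target and whether all patients without pneumonia serve as controls. Then, in Protocol section 4 and the SAP:

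1. Replace m = 0.9 with m = 9, the ratio that 10% implies.
2. State that the test is two-sided, if it is.
3. Restate the group sizes, the interval width (saying whether at rounded or unrounded n) and the expected total enrolment:
   - **Corrected calculation:** 8 cases and 72 controls, 80 patients at exactly 10%, width 39.4 (40.3 unrounded); or about 90 patients to hold averaged power at 0.9.
   - **16 cases kept:** about 160 patients on average with about 144 controls, noting that 160 patients give only a 0.54 chance of at least 16 cases.
4. Delete the figure of 14 controls unless a subset is to be analysed. If it is, justify the subset's ratio as a sampling choice, not as a result of the 10% rate, and state how the controls are drawn from the patients without pneumonia.
5. Only if 30 patients in total were intended, lower the stated power to about 0.4.

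The cost is one corrected paragraph in each document and the sponsor's decision. No planned measurement or analysis has to change, although the case target chosen determines how many events the ROC and regression analyses will have.

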#### 8. Study plan:

Timepoint 1, preoperative:

Obtaining informed consent and inclusion in the study, blood draw  
Preoperative chest X-ray (clinical routine)

Timepoint 2, Operative Intervention:

Blood draw, asservation of alveolar secretions (endobronchial after intubation)

Timepoints 3.1 – 3.n, postoperative (daily):

Blood draw, asservation of alveolar secretions (if ventilated) chest X-ray (if clinically needed)

Timepoint 4, Discharge:

Final evaluation

Patients will be included in the study, if fulfilling the inclusion criteria and missing exclusion criteria. Written informed consent will be obtained from the patients.

Patients will be pseudonymised by assigning a sequential number.

Anonymization of the patients cannot be considered in such a conceived study, since the change of personal data makes an assignment of essential clinical course data impossible.

Blood draws:

Blood will be collected by puncture or draw by venous or arterial catheter during the clinical routine for determination of leucocyte count, CRP value, and blood sugar. Blood samples will be analyzed in the in-house laboratory. Blood sugar levels are additionally measured in the intensive care unit using a blood gas analyzer.

In addition, one blood sample EDTA and one serum are collected (9 mL each). The centrifugation and aliquoting of the obtained plasma and serum samples will be spinned down and aliquoted. The samples are stored at -80 ° C in the laboratory rooms of the Cardiac Surgery Department for later analysis.

X-ray:

The evaluation of the radiological images of the chest is carried out as part of the clinical requirements. There is no additional requirements of radiological examinations due to the study.

Endobronchial sampling:

The endobronchial sampling of alveolar fluid will be performed by utilizing the inserted tube and aspiration with a suction catheter. Two samples are taken. The first sample is sent to the in-house laboratory immediately after sampling for microbiological analysis. The second sample is stored at -80 ° C in the premises of the cardiosurgical research department until later analysis.

Clinical evaluation/examination:

There is a daily clinical examination of the patients for signs of pneumonia.

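### Patients found ineligible after inclusion may be removed at any time, even once pneumonia status is known, and leave the study documentation uncounted, so selective loss from the primary incidence could not be detected in the study data

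*Protocol*

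**What the plan says.** Protocol section 3 sets the endpoint: "The primary endpoint of the study is the incidence of pneumonia".

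Protocol section 6 governs removal after inclusion. The reasons are restricted: "Reasons for a subsequent exclusion of the patient only apply if subsequently it is determined that not all inclusion criteria are met", or where there were "exclusion criteria that were not initially recognized". The section then adds: "These patients are also excluded from the documentation".

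Protocol section 8 gives the timing. Timepoint 1, before surgery, is "Obtaining informed consent and inclusion in the study, blood draw". After surgery, "There is a daily clinical examination of the patients for signs of pneumonia", and the final evaluation is at discharge. On identification, "Patients will be pseudonymised by assigning a sequential number".

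Section 5 describes the population as "Patients undergoing elective cardiac surgery matching inclusion and exclusion criteria"; the criteria themselves are not listed in the text available for this review. The SAP does not mention exclusion after inclusion, define an analysis population, or plan an analysis with such patients put back.

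**The concern.** Removing patients who never met the criteria is a common choice in an observational cohort, and can be defended when each removal is counted and explained. Two features of section 6 together take that defence away.

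First, there is no cut-off. A patient included before surgery can be removed on the ward or at discharge, when those deciding may know whether pneumonia has developed. Second, the patient leaves the documentation as well, and nothing asks for a count, date, reason or outcome status.

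The plausible route to bias is uneven scrutiny, without any deliberate selection. A patient who becomes ill has the history and chart read more closely, so an overlooked exclusion criterion may be more likely to surface. If that happens, cases leave at a higher rate than controls and the reported incidence is too low. Because the endpoint is a proportion, each removal acts on numerator and denominator together. The rule also removes the information with which the study could show that exclusions were few, or unrelated to outcome.

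**Working it through.** **Inputs.** From Protocol section 4, repeated in the SAP: expected pneumonia incidence 10%; 16 patients with pneumonia and 14 controls; α = 0.01; power 0.9; δ = 30 mg/dL; σ = 20 mg/dL; m = 0.9. Assumed here: 160 enrolled, and 1 to 3 patients removed.

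**Step 1. The plan's own figure.** Two-sample t-test, two-sided α = 0.01, noncentral t. With 16 and 14 patients the noncentrality is 30 / (20 × √(1/16 + 1/14)) = 4.10 on 28 degrees of freedom, and the power is 0.899. With 0.9 × 16 = 14.4 controls it is 0.905; with 15 cases and 13.5 controls it is 0.879. So 16 cases is the smallest number reaching 0.9 at m = 0.9. The stated size reproduces, and this point does not depend on any error in it.

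**Step 2. An enrolment figure for illustration.** The documents give no enrolment total for the incidence. At the stated 10%, 16 cases would arise among about 16 / 0.10 = 160 patients, leaving 144 without pneumonia. This is an assumption.

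**Step 3. Effect of removals on the incidence.** If k cases are removed, the incidence is (16 − k) / (160 − k). If k controls are removed, it is 16 / (160 − k).

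| k | Cases removed | Controls removed |
|---|---|---|
| 0 | 16/160 = 10.0% | 16/160 = 10.0% |
| 1 | 15/159 = 9.4% | 16/159 = 10.1% |
| 2 | 14/158 = 8.9% | 16/158 = 10.1% |
| 3 | 13/157 = 8.3% | 16/157 = 10.2% |

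**Step 4. Why cases dominate.** With incidence p among N patients, removing one case changes the incidence by −(1 − p)/(N − 1) = −0.9/159, about −0.57 percentage points. Removing one control changes it by +p/(N − 1) = +0.1/159, about +0.06 points. A lost case therefore weighs nine times as much as a lost control.

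**Step 5. When there is no bias.** If cases and controls are removed in proportion, one case for every nine controls, the incidence does not move: (16 − 1) / (160 − 10) = 15/150 = 10.0%. Bias requires that removal be related to pneumonia status. Checking this needs the number removed in each group, which is what section 6 does not keep.

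**The case against.** The strongest reply is that section 6 is already restrictive. It admits only eligibility failure, so it bars removal at discretion or because of outcome. Since inclusion is preoperative, a criterion overlooked at inclusion most naturally means a fact already present before surgery. This stands in part: the reasons are limited. But the tie to preoperative facts is only implied, and no limit is placed on when the check may be made or on who makes it with what knowledge.

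Second, the shift is small. The exact 95% interval for 16/160 is 5.8% to 15.7%, every value in the table lies inside it, and the documents set no precision target or threshold that would be crossed. This is fair as to size. It does not remove the point, because that interval reflects sampling error only and makes no allowance for selective loss.

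Third, with the criteria not listed in the available text, one cannot say whether any of them would surface preferentially in patients with pneumonia. This also stands: the mechanism is plausible, not demonstrated.

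A reader might infer several stronger things that the documents do not support:

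- That the records are destroyed, or that no trace could survive. The text says only that patients leave the documentation. A gap in the sequential numbers, and routine laboratory, microbiology and X-ray results, may remain, although nothing requires a gap to be counted or explained.
- That the glucose comparison would have an inflated false-positive rate. Closer scrutiny of ill patients selects on pneumonia status. In simulation, removing 1 to 3 cases without regard to glucose left the error rate at 1.0% and the mean shift at about zero. Inflation arises only if the cases removed are those with the lowest glucose, and nothing in the documents suggests this.
- That the study would lose material power. That depends on how many controls are assumed, and it is no argument for the change, since the main analysis may still leave ineligible patients out.

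**Conclusion.** The point holds as a weakness in traceability with a possible bias of modest size. Section 6 permits exclusion for ineligibility after pneumonia status is known, and requires no record of how many patients left, when or why. If eligibility failures are found more often in patients who become ill, the primary incidence is biased downward and the study data could not reveal it. On the illustrative basis of 160 enrolled and 16 cases, each case removed lowers a 10% incidence by about 0.6 percentage points, to 8.3% after three; each control removed raises it by about 0.06.

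This rests on three assumptions: the enrolment figure, the number of removals, and uneven scrutiny by outcome. The documents establish none of them. They show that selective removal is possible and would go unseen in the study data. They do not show that it happened, and a reader should not infer that it did.

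**What to change.** Replace the last sentence of Protocol section 6 with text such as:

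> Patients found ineligible after inclusion stay in the documentation under their sequential number, with the date and reason. Eligibility is judged only on facts that existed before surgery. The number excluded is reported by pneumonia status, and the incidence and the glucose comparison are repeated with these patients included.

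Add the reporting and the repeated analysis to the SAP under Documentation / Evaluation, which does not address these patients at present.

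The cost is a few extra pseudonymised records and one sensitivity analysis. No new patients, samples or examinations are needed. A separate assessor unaware of pneumonia status is not asked for: it could need extra staff at a single centre, and the restriction to preoperative facts, with dates, reasons and counts by outcome, makes the exclusions open to checking.

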Statistical Analysis Plan

Development of Pneumonia Due to Alveolar Glucose Levels in Systemic Hyperglycemia

Version: 1

Date: 08/01/2017

Sample size calculation:

The sample size estimate was based on the assumption that in the investigated patient population the occurrence of pneumonia could be expected in 10% of the patients. Thus, for an unconnected sample, a ratio (m) of 0.9 controls per incidence of pneumonia. In a previous study (Bacterial respiratory tract infections are promoted by systemic hyperglycemia after severe burn injury in pediatric patients, Kraft et al., Burns, 2014, May), it was found that the mean values (δ) of both groups for glucose differed by about 30 mg / dL in the mean with a standard deviation (σ) of 20 mg / dL. Under the same conditions, 14 controls and 16 patients with pneumonia are needed to reject the null hypothesis with a probability (power) of 0.9.

The occurrence of the first type error (α) was set at 0.01. Design: Independent

$\alpha = 0.01$; power = 0.9; $\delta = 30$; $\sigma = 20$; $m = 0.9$; $n = 16$;

t-test confidence interval width = 40.68604

Calculated with PS Power and SampleSize Calculator Version 3.0,
<http://biostat.mc.vanderbilt.edu/PowerSampleSize>

Documentation / Evaluation:

All study-relevant data are recorded in the provided documentation sheets by the responsible study physicians and, if necessary, the study assistants. The study forms are digitized and stored in the in-house EDP system in compliance with the safety guidelines using the programs Microsoft Excel® and Access®. Radiological images are stored in digital form, preferably in TIFF or raw data format. The statistical analysis is carried out by means of the programs Sigmaplot® and Sigmaplot®.

The statistical evaluation is carried out on the one hand with regard to the cut-off value of the glucose threshold of the lung by means of Receiver Operating Characteristic (ROC). This is used to validate our findings in comparison to the already existing preliminary studies. The evaluation of dichotomous variables is performed by Chi Square Test or, if necessary, by Logistic Regression Analysis. Constant features are compared using Student's t-test, analysis of variance between the groups. With regard to the presence of disturbing variables between the two groups, the formation of subgroups, possibly a matching by means of a propensity score, is planned.

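### Blood and alveolar glucose are sampled at shared timepoints, but no pairing rule is set and no pre-specified analysis uses both, so the plan does not separate an alveolar effect from systemic hyperglycemia

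*Protocol*

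**What the plan says.** The title of both documents poses the question as "Development of Pneumonia Due to Alveolar Glucose Levels in Systemic Hyperglycemia". That names two glucose compartments and an outcome. Protocol section 3 makes the incidence of pneumonia the primary endpoint.

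**Sampling (Protocol section 8).** At operation: "Blood draw, asservation of alveolar secretions (endobronchial after intubation". On each postoperative day: "Blood draw, asservation of alveolar secretions (if ventilated) chest X-ray (if clinically needed". Blood glucose is one of the routine tests, and "Blood will be collected by puncture or draw by venous or arterial catheter during the clinical routine". There is a second source: "Blood sugar levels are additionally measured in the intensive care unit using a blood gas analyzer". For the aspirate, "The second sample is stored at -80 ° C in the premises of the cardiosurgical research department until later analysis". No clock time, maximum interval or matching rule is given for the two fluids. Nothing says whether the laboratory or the blood gas value goes with an aspirate.

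**Analysis (Protocol section 7; SAP, Documentation / Evaluation).** "The statistical evaluation is carried out on the one hand with regard to the cut-off value of the glucose threshold of the lung", by ROC. The next sentence says that this serves to check the results against preliminary studies. In the SAP, "Constant features are compared using Student's t-test, analysis of variance between the groups". Logistic regression is available for dichotomous variables where needed. Imbalance between groups is to be handled by subgroups and perhaps propensity-score matching. No covariate is named for either. No correlation, ratio, joint model or adjustment of one glucose measure for the other appears.

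**The concern.** If alveolar glucose follows blood glucose, and blood glucose is what differs between patients with and without pneumonia, then alveolar glucose differs between them too. A one-marker ROC or t-test on alveolar glucose would look positive even if the lung compartment played no part. An analyst could follow the plan exactly and report an alveolar association that blood glucose alone had produced.

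The missing pairing rule bears on any later attempt to adjust. A blood value taken at a different point of the day is a poorer stand-in for blood glucose at the time of the aspirate, so adjustment for it is incomplete. Collection times that are not recorded as samples are taken may not be recoverable afterwards.

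**Working it through.** **1. The plan's own figure.** Inputs from Protocol section 4: difference 30 mg/dL, SD 20 mg/dL, alpha 0.01, power 0.9, 0.9 controls per case. The standardised difference is 30/20 = 1.5. A two-sided two-sample t-test (noncentral t) has power 0.905 with 16 cases and 14.4 controls, 0.899 with 16 and 14, and 0.879 with 15 and 13.5. The stated 16 and 14 reproduce. This calculation covers one glucose variable compared between two groups. It does not cover an alveolar effect adjusted for blood glucose.

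**2. What one marker shows when it has no effect of its own.** Assumptions that are not in the documents:
- the 1.5 SD difference applies to blood glucose (section 4 does not state the compartment);
- both markers are normal with equal within-group variance;
- alveolar glucose is linked to pneumonia only through its within-group correlation r with blood glucose.

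In SD units, alveolar = r × blood + √(1 − r²) × noise, so the induced alveolar difference is d = 1.5r. The area under the ROC curve is AUC = Φ(d/√2). The rejection rate of the unadjusted alveolar t-test is its noncentral-t power at d, with 16 and 14 patients and two-sided alpha 0.01.

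| r | d = 1.5r | AUC | Unadjusted t-test rejects |
|---|---|---|---|
| 0.3 | 0.45 | 0.62 | about 8% |
| 0.5 | 0.75 | 0.70 | about 26% |
| 0.7 | 1.05 | 0.77 | about 55% |
| 0.9 | 1.35 | 0.83 | about 81% |

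Simulation under the same assumptions (6,000 studies per r) agrees with the last column to within about one percentage point. When alveolar glucose is regressed on group and the paired blood glucose, rejection of the group term returns to about 1%, the nominal level, at every r.

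**3. What the joint analysis costs if the alveolar effect is real.** Reverse the assumption: only alveolar glucose differs, by 1.5 SD, and blood follows it with correlation r. The same adjusted linear comparison at alpha 0.01, by simulation, detects the alveolar effect as follows.

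| r | 16 vs 14, no measurement error | 16 vs 14, aspirate 50% reliable | 16 vs 144, no measurement error |
|---|---|---|---|
| 0.5 | about 68% | about 29% | about 99% |
| 0.7 | about 43% | about 11% | about 89% |
| 0.9 | about 11% | about 2% | about 38% |

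The unadjusted test at 16 vs 14 has the planned 90%. In the middle column, blood glucose is wrongly credited in about 5%, 11% and 27% of studies. The 50% reliability is an assumption. The 16 vs 144 split follows from the plan's 10% incidence: 16/0.10 = 160 patients, of whom 144 are controls.

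**The case against.** Several stronger readings are tempting, and the documents do not support them.

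- **That the samples are unpaired.** A reader might infer this from the reference to routine blood draws. Section 8 lists both samples under the same timepoints, at operation and daily while the patient is ventilated, and adds blood gas glucose in intensive care. What is missing is a window and a rule. That values lie hours apart would be inference, since no intervals are given.
- **That the study cannot tell the two effects apart.** Same-timepoint samples would exist, and logistic regression or propensity matching could include blood glucose. The gap is that neither is committed to and no covariate is named.
- **That the study will report a causal alveolar effect.** The causal phrasing is in the title. The primary endpoint is pneumonia incidence, and no rule in the plan ties a conclusion to the ROC. A one-marker ROC is a legitimate way to find a predictive cut-off, whatever the mechanism. This stands, and it is why the ROC should be kept.

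The illustration is also assumption-bound. The documents give no correlation, and at r = 0.3 the induced signal is modest. Samples far apart in time would show a weaker observed correlation. Finally, making the joint model the sole basis for any alveolar statement could hide a true effect, as step 3 of the working shows. That objection stands and limits the fix.

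**Conclusion.** The point holds in this form: the samples share timepoints without a pairing rule, and no pre-specified analysis uses both markers, so the planned ROC and t-test leave an alveolar effect unseparated from systemic hyperglycemia. The conditional tools do not close the gap, because the plan can be followed in full without ever adjusting for blood glucose.

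Under the stated assumptions, an alveolar marker with no effect of its own would show an AUC between about 0.62 and 0.83 for correlations from 0.3 to 0.9. These figures illustrate the size of the problem and do not forecast this study's results. That no specified analysis combines the markers rests on the text alone and needs no assumption.

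The change should be made, but it is no reason to discard the planned analyses.

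**What to change.** **Protocol section 8.** Record the time of each aspirate. Pair it with the nearest blood glucose from the same timepoint, whether routine draw or intensive-care blood gas value, and record the source and the interval.

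**Protocol section 7 and SAP.** Keep the ROC as the cut-off analysis. Pre-specify two secondary analyses:
1. a mixed model of alveolar glucose on paired blood glucose, with a patient random effect;
2. a logistic model for pneumonia with both markers, its AUC compared with that of blood glucose alone. Name in advance which pair per patient enters, because the number of aspirates depends on time ventilated.

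Describe the ROC and t-test results as unadjusted associations. Report the joint model beside them before claiming any effect independent of blood glucose.

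**Cost.** Wording in both documents, plus times and intervals on the documentation sheets. No extra sample is needed, and logistic regression is already named. The statistical price is imprecision: with about 16 events and strongly correlated markers the joint estimate will be wide, and measurement error in the aspirate can shift credit to blood glucose. The SAP should therefore say that a null joint result is not to be read as no alveolar effect.
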